### **5.5.2. Mini-Hyper-CVD Regimen**

#### **5.5.2.1. General Considerations**

- The Mini-hyper-CVD (odd cycles) will alternate with methotrexate and cytarabine (even courses) administered on Day 28 (if count recovery allows) or later day cycle (as count recovery allows).
- Anti-emetic therapy with each course of intensive chemotherapy as needed.

- Filgrastim (G-CSF) will be administered with each course after the completion of chemotherapy. Peg-filgrastim may replace filgrastim (G-CSF). Biosimilars may be used for filgrastim or peg-filgrastim.
- Next cycle may be started when granulocytes  $> 1.0 \times 10^9/L$  and platelets  $\geq 50 \times 10^9/L$ . Cycles may be started with dose reductions prior to full platelet recovery, if the treatment is delayed (e.g., greater than 28 days from last cycle).
- Prophylactic antibiotics may be given with each course until neutrophil recovery to  $0.5 \times 10^9/L$  or greater (or other antibiotics if being treated for active infection). Suggestions include: Levaquin 500 mg orally daily; trimethoprim-sulfamethoxazole double-strength one tablet orally twice daily; or other appropriate antibacterial agent. Caspofungin or another appropriate antifungal agent. Valacyclovir 500 mg orally daily; or acyclovir 200 mg orally twice daily; or another appropriate antiviral agent.
- Omit azoles on Day -1, same day, and day after vincristine.
- In general, 8 cycles of chemotherapy (4 Mini-hyper-CVAD, 4 methotrexate plus cytarabine) will be administered in approximately 28-day intervals (depending on the recovery of blood counts). Thereafter, maintenance therapy with DS-1594b in combination with, vincristine and corticosteroids may be continued for up to 2 years of maintenance. Modifications thought to be in the best interest of the subject are allowed after discussion with the Principal Investigator. Subjects will be followed indefinitely for relapse and survival.
- For subjects with CD20 expression ( $\geq 20\%$  by flow cytometry) Rituximab 375 mg/m^2 may be added on Days 1 ( $\pm 3$  days) and 11 ( $\pm 3$  days) of Cycles 1 and 3, and on Days 1 ( $\pm 3$  days) and 8 ( $\pm 3$  days) of Cycles 2 and 4. For subjects receiving rituximab all therapy can be moved back 1 day if needed (i.e. Day 1 starts Day 2, Day 2 starts Day 3, etc.).
- Methotrexate dose regimen will be adjusted as indicated below for pleural effusions.

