- Changes in drug dose and/or schedule must be discussed with and approved by the investigator, or they're representative prior to initiation, and will be documented in the subject record.
- Subjects with an objective response at completion of active study treatment will be followed for survival at the site every 3 to 6 months for up to 5 years after completion of active treatment and while still on study. If the subject is unable to return to the site, the duration visits may be conducted via telephone.

- Data regarding adverse events will be collected during the study. Protocol specific data will be entered into the electronic case report form (eCRF). The eCRF used for this protocol will be Prometheus. AEs will be recorded in the Case Report Form.
- Treatment may be discontinued for a variety of reasons, including subject withdrawal, investigator decision, and reasons specified by the protocol. Reasons for discontinuation of treatments are described in section 10.0.

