#### **9.4.6. Efficacy Analyses**

The efficacy analyses will be carried out for both the Efficacy Analysis Set and the Safety Analysis Set. Subjects with prior treatment with other menin inhibitors will be analyzed separately for efficacy.

For the primary efficacy analysis, the primary efficacy outcome (CR + CRh rate for Cohorts A, B, C and CR+CRi rate for Cohort D) will be estimated along with the 95% credible interval for each cohort. If the study cohort is not stopped early, assuming 11 of the 26 subjects achieve the response (CR + CRh for Cohorts A, B, C and CR+CRi for Cohort D), the 95% credible interval for the response rate will be (25%, 61.3%). The same method will be used for other binary efficacy outcomes in Phase 1 and Phase 2, including rate of durable transfusion independence, the 4- and 8-week mortality rates, the rate of subjects able to proceed to HSCT, and the MRD rate at the first response and at the best response. The time to event outcomes, including DOR, time to first response, time to best response, median duration to HSCT, EFS and OS, will be estimated using the Kaplan-Meier method. For the exploratory analysis, logistic regression models and Cox proportional hazards models will be fitted to correlate clinical factors, expressions of immune markers with efficacy outcomes. OS time will be calculated from the

date of the treatment start to the date of death or to the date of last follow-up if patients are alive at the time of data collection. Patients alive will be censored at the analysis. EFS will be calculated from the date of start treatment to the date of disease relapse or date of death whichever occurs first, or to the date of last follow-up for patients who are alive and have no relapsed disease at the time of data collection. Patients who are alive and have no relapsed disease will be censored at the analysis.

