																										dosing) and Table 15 ( Table 15 (QD dosing) for timing of sampling, Table 19 ( Table 19 for food-effect sub-study, and Table 17 ( Table 17 and Table 18 ( Table 18 for DDI sub-study. Visit windows not applicable for PK sub-studies.		
Assess Response and Relapse											X					X			X			X*	X			*Day 28 (±4) of each cycle.		
Biomarker/ PD Blood Sample	X	X		X	X		X	X		X		X		X		X		X		X		X						
Dispense DS-1594b		X									X				X			X		X		X			Continuous Dosing Every 12h (+/- 4h); Administer morning dose in clinic on PK days			
Administer morning dose of DS-1594b at site		X	X	X	X	X*	X			X				X			X		X		X**				*For daily dosing only ** Cycles 5 and 6 only. Additional instruction for sub-studies:			

Formatted: C-Hyperlink, Font: 8 pt

Phase 1 Dose Escalation Schedule of Events																								
Procedure	SCR	C1							C2					C3			C4		Cx		30D FU	LT FU	Comment	
Day	-14	1	2	5	8	9	15	16	21	28	1	8	15	21	28	1	15	28	1	15	EOT	30D FU	LT FU	Comment
Window				±1D	±1D	±1D	±1D	±1D	±1D	±4D	±4D	±1D	±1D	±1D	±1D	±4D	±4D	±4D	±4D	±4D	+7D	±14D		
																							For DDI sub-study, administer morning dose on-site on PK days (C1D18, C1D19, C2D10, C2D11). See Table 17 and Table 18 . For food effect sub-study, administer morning dose on-site on PK days (C1D18, C1D19); see Table 19 .	
Collect Returned DS-1594b Assess Compliance									X					X			X	X						
Survival FU, Subsequent Antileukemic Treatments & Outcomes																			X	X	Every 3 months in LTFU			

Formatted: C-Hyperlink, Font: 8 pt

Formatted: C-Hyperlink, Font: 8 pt

Formatted: C-Hyperlink, Font: 8 pt

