Creatinine Kinase	X	X	Weekly						≥ 1 per cycle			X						Fractionated if >ULN						
Troponin	X																	Monitor on treatment, if clinically indicated						
Urinalysis	X	X	≥ 1 per cycle										X					Screening procedures should be done 3 days before C1D1.						
Pregnancy Test	X	≥ 1 per cycle										X	X				For women of childbearing potential, document the results							

Phase 2 Cohorts A & B																			
Procedure	SCR	C1						C2		C3		C4		Cx		EOT	30D FU	LT FU	Comment
Day	-14	1	2	8	9	15	28	1	28	1	28	1	28	1	28				
Window			$\pm 1D$	$\pm 1D$	$\pm 1D$	$\pm 1D$	$\pm 4D$	$\pm 3D$	$+7D$	$\pm 14D$									
Plasma alpha-MSH	X						X			X*			X*		X			* Once every 3 cycles beginning at Cycle 3	
Fasting morning ACTH, aldosterone, renin, and cortisol	X						X			X*			X*		X			* Once every 3 cycles beginning at Cycle 3	
HIV Ab Test	X																	If required by local regulations; $\leq 28$ days of first dose	
HBsAg, HC Ab	X																	$\leq 28$ days of first dose	
PK		X	X*	X	X*	X		X		X		X		X**				*For daily dosing only **Cycles 5 and 6 only See Table 16 for sampling times	
Assess Response and Relapse							X		X		X		X		X*	X		*Day 28 ( $\pm 4$ ) of each cycle.	
Biomarker/ PD Blood Sample	X	X		X		X		X		X		X				X			
Dispense DS-1594b		X						X		X		X		X				Continuous Dosing Every 12h ( $\pm 4$ h); Administer morning dose in clinic on PK days	
Administer morning dose of DS-1594b at site		X		X		X		X		X		X		X*				*Cycles 5 and 6 only	
Collect Returned DS-1594b, Assess Compliance								X		X		X		X		X			

Formatted: C-Hyperlink, Font: 8 pt

Phase 2 Cohorts A & B																			
Procedure	SCR	C1						C2		C3		C4		Cx		EOT	30D FU	LT FU	Comment
Day	-14	1	2	8	9	15	28	1	28	1	28	1	28	1	28				
Window			±1D	±1D	±1D	±1D	±4D	±3D	+7D	±14D									
Survival FU, Subsequent Anti-leukemic Treatments & Outcomes																X	X	Every 3 months in LTFU	

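### EFS is censored at the last follow-up contact, but Phase 1 and Cohorts A–C have no scheduled relapse assessment after treatment beyond one 100-day clinical visit

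*Combined protocol and SAP*

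**What the plan says.** **The analysis rule.** Section 9.4.6 gives the start and the events in one clause: "EFS will be calculated from the date of start treatment to the date of disease relapse or date of death whichever occurs first". For a subject with neither event, a second clause sets where the clock stops: "or to the date of last follow-up for patients who are alive and have no relapsed disease at the time of data collection". OS runs from "date of the treatment start to the date of death or to the date of last follow-up if patients are alive". The two endpoints share one censoring date, and nothing ties EFS to the last disease assessment. Duration of response is listed for Kaplan-Meier estimation in the same section, with no event or censoring rule.

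**The schedule.** In Table 33 the row "Assess Response and Relapse" carries six marks, which fit Day 28 of Cycles 1, 2, 3, 4 and later cycles, plus end of treatment. The same row in Tables 32, 34 and 35 also runs out at end of treatment (after maintenance in Cohort D). From then on, the long-term follow-up row is "Survival FU, Subsequent Antileukemic Treatments & Outcomes", every 3 months.

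**The follow-up text.** Section 8.7 says that subjects with an objective response "will be followed for survival at the site every 3 to 6 months for up to 5 years after completion of active treatment". It then allows a fallback for those who cannot travel: "If the subject is unable to return to the site, the duration visits may be conducted via telephone". Section 8.9.1 adds one 100-day clinic visit with a clinical evaluation and physical examination, with a local physician or a telephone call as fallback. Section 8.8.4 describes how a relapse suspected at follow-up is confirmed and dated. Only the Cohort D regimen section, 5.5.2.1, goes further: "Subjects will be followed indefinitely for relapse and survival".

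**The concern.** A survival contact tells the analyst that the subject is alive. It does not tell the analyst that the leukemia has not returned. A subject who stops treatment in remission (for transplant, toxicity or by choice), relapses three months later and is reached alive at month 12 counts as event-free at month 12 unless the relapse was separately recorded. The error runs in one direction, towards longer EFS. It grows with the number of responders who leave treatment in remission, and proceeding to transplant is itself a secondary endpoint in both phases.

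At stake are EFS and, if the same rule is carried over, duration of response. A relapse date that is not collected at the time may be hard to recover later.

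**Working it through.** The plan states no EFS median, rate or event count, so there is no figure to reproduce. The check is an illustration of size.

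**Inputs**
- Response rate 40%: the target in Section 9.3.
- Median time to relapse in responders 6, 9 or 12 months from treatment start: assumed. Section 2.1 cites a median response duration of 9 months after salvage.
- Median survival after relapse 4 or 6 months, and non-responder median survival 5 months: assumed, within the 4–7 month OS in Section 2.1.
- Share of responders who would leave treatment in remission, 25% or 50%, at a time uniform on 2–6 months: not in the documents, assumed.
- Exponential times; data cut-off uniform on 12–24 months.

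**Who is affected.** Section 8.8.4 defines relapse only after a remission, and Section 9.4.6 does not make treatment failure an event. A non-responder's EFS is therefore time to death and is unaffected.

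**Formula.** With no post-treatment detection, the excess in 12-month EFS is the probability of stopping in remission, relapsing after the stop and before month 12, and being alive at month 12. Let λ = ln 2 / (median relapse), μ = ln 2 / (median post-relapse survival), p = share stopping, u = stop time and r = response rate. Then

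excess = r × p × [λ/(μ−λ)] × e^(−12μ) × {e^(12(μ−λ)) − mean over u of e^(u(μ−λ))}

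**One case by hand** (relapse median 9, post-relapse median 6, p = 0.5):
- λ/(μ−λ) = (1/9)/(1/6 − 1/9) = 2
- e^(−12μ) = 2^(−12/6) = 0.25
- e^(12(μ−λ)) = 2^(12/18) = 1.5874
- Mean over u from 2 to 6 = (2^(6/18) − 2^(2/18)) / (4 × ln 2/18) = (1.2599 − 1.0801)/0.1540 = 1.168
- Responders only: 0.5 × 2 × 0.25 × (1.587 − 1.168) = 0.105, or 10.5 points
- Whole cohort: 0.4 × 0.105 = 0.042, or 4.2 points
- True 12-month EFS: 0.4 × 2^(−12/9) + 0.6 × 2^(−12/5) = 0.159 + 0.114 = 0.272, so the rule as written gives about 0.314

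**Full grid**, by Kaplan-Meier simulation (400,000 subjects per case, no post-treatment detection). Ranges cover post-relapse medians of 4 and 6 months. The last column censors at end of treatment without collecting relapse status.

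| Relapse median (months) | Share stopping | Whole cohort, median EFS (months) | Whole cohort, 12-month EFS (points) | Responders, 12-month EFS (points) | Whole cohort, censored at end of treatment (points) |
|---|---|---|---|---|---|
| 6 | 25% | +0.14 to +0.15 | +1.9 to +2.3 | +4.7 to +5.8 | −0.3 |
| 6 | 50% | +0.30 to +0.32 | +3.7 to +4.6 | +9.2 to +11.6 | −0.6 |
| 9 | 25% | +0.18 to +0.20 | +1.7 to +2.1 | +4.3 to +5.3 | −0.9 to −1.0 |
| 9 | 50% | +0.40 to +0.45 | +3.4 to +4.2 | +8.5 to +10.5 | −2.1 |
| 12 | 25% | +0.21 to +0.23 | +1.5 to +1.8 | +3.8 to +4.6 | −1.4 |
| 12 | 50% | +0.43 to +0.49 | +3.0 to +3.7 | +7.5 to +9.3 | −3.2 |

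If half the relapses are caught on time, the whole-cohort rise is 0.7–2.3 points at 12 months and 0.07–0.24 months on the median.

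**Different assumptions.** Another run took response at 2 months, relapse median 9 months after response, non-responder median 4 months, post-relapse median 3.8 or 7 months, 10–50% stopping, and detection of none or of 75% with a 2-month delay. It gave a whole-cohort rise of 0.3–4.3 points at 12 months and about 0.2 months or less on the median. The responder rise was about 1–11 points.

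**The case against.** A reader might infer that relapse is not looked for at all once treatment ends, and that EFS is therefore overstated by a tenth to a third. The documents do not support that.

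- **Detection is partial, not absent.** The 3-monthly contact asks about later antileukemic treatment and outcomes, which would expose many relapses. Section 8.9.1 keeps subjects on study and adds the 100-day visit. Section 8.8.4 expects relapse to be suspected from follow-up examination or blood counts and dates it to the first suggestive test. In Section 8.7 the telephone is a fallback. Cohort D text commits to relapse follow-up. All of this stands and rules out zero detection as the expected case. It does not close the gap: none of these sections sets a continuing post-treatment relapse assessment, and the long-term row names no relapse date. A relapse inferred from new therapy may be dated late.
- **The large percentages belong to responders.** A rise of a tenth to a third in the median appears only when responders are analysed alone with nothing detected. EFS is analysed in all treated subjects. This stands.
- **Death remains an event**, so a missed relapse is usually delayed, not lost. This stands and is built into the figures.
- **Little hangs on EFS.** It is secondary, with no test, threshold or decision rule. The primary response rate and the stopping boundaries are untouched. This stands.
- **Censoring at end of treatment has its own bias.** It removes only responders in remission, so the rest of the cohort looks worse. This stands and determines the order of the fix.

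The schedule tables are imperfectly extracted. The absence of a relapse mark under follow-up is read from the visible row layout, which is consistent across all four tables.

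**Conclusion.** The concern holds in a conditional form. Section 9.4.6 counts time to the last contact as event-free, while the schedule for Phase 1 and Cohorts A–C provides only one clinical visit at which relapse might be found after treatment. Cohort D has a commitment without a schedule. EFS is biased upward to the extent that relapses after stopping in remission are missed or dated late, and the bias is zero if they are fully and promptly recorded.

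With no detection and the assumptions above, the whole-cohort effect is about 0.1–0.5 months on the median and about 2–4 points at 12 months (1.5–4.6 across the grid). It is about half that if half the relapses are caught. Among responders it is about 4–11 points at 12 months (3.8–11.6 across the grid). That is the relevant scale for duration of response if the same rule is applied. The share stopping in remission and the share of relapses missed drive these figures, and the documents give neither. The change should be made because it is cheap and the data are collected prospectively. No primary conclusion depends on it.

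**What to change.** 1. **Collect the data first.** Add relapse status, date and basis to the existing 3-monthly long-term contact, in all cohorts, for every subject who left treatment in remission.
2. **Then set the censoring rule.** In Section 9.4.6, censor EFS and duration of response at the last date on which relapse status was ascertained, counting those contacts. State the event definition for duration of response, and how transplant and new antileukemic therapy are handled in both endpoints.
3. **Reconcile the follow-up provisions** in Sections 5.5.2.1, 8.7, 8.8.4 and 8.9.1 with Tables 32–35, so that one statement says what is followed after treatment, in whom and how often.

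The cost is one eCRF item at a contact already planned, a short addition to Section 9.4.6, and slightly earlier censoring for some subjects. No extra visits or marrows are needed. Step 2 should not be reduced to censoring at end of treatment without step 1: in the runs above that lowered whole-cohort 12-month EFS by 0.3 to 3.2 points, in places as much as the rule as written raises it.

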#### **9.4.7. Safety Analyses**

Safety analyses will be performed in the safety population. AEs that occur or worsen relative to the pre-treatment state after the start of study treatment and within 30 days of the last dose of study drug (TEAEs) will be tabulated. AEs will be coded using the Medical Dictionary for Regulatory Activities (MedDRA) terminology and tabulated by body organ group using the MedDRA system organ class (SOC) and by AE term using preferred terms (PTs).

Safety evaluation will include DLTs, serious adverse events, treatment-emergent adverse events, physical examination findings (including ECOG performance status), vital signs measurements, standard clinical laboratory parameters, and ECG parameters (including QTcF).

Safety analyses in general will be descriptive and will be presented in tabular format with the appropriate summary statistics by dose level and in total for Phase 1, and by cohort and in total for Phase 2, unless otherwise stated. Only the treatment emergent assessments (i.e., assessments within the 30 days of last study drug dose) would be used in the analyses unless otherwise specified.

The summary of DLTs in the Dose Escalation parts will be performed based on the DLT Evaluable Set. All other safety summaries and analyses will be performed based on the Safety Analysis Set and subjects will be analyzed according to the actual treatment they received.

##### **9.4.7.1. Dose-Limiting Toxicities**

For Phase 1 (Dose Escalation), the number of DLTs identified among the DLT evaluable subjects in the DLT Evaluable Set will be listed and summarized for each dose cohort and in total by the worst NCI-CTCAE grade, system organ class (SOC), and preferred term (PT).

##### **9.4.7.2. Adverse Events**

Adverse events will be assigned grades based on NCICTCAE v5.0.

A TEAE is defined as those AEs with start or worsening date during the treatment period (from first dose date until 30 days after the last dose of study medication). It includes AEs having been absent at pre-treatment; or reemerges during treatment, having been present at baseline, but stopped prior to treatment; or worsens in severity after starting treatment relative to the pre-treatment state, when the AE is continuous.

###### **9.4.7.2.1. Summary of Treatment-Emergent Adverse Events**

The number and percentage of subjects with the following TEAEs will be summarized:

1. TEAEs by SOC, preferred term, and worst CTCAE grade;

2. Study-drug-related TEAEs by SOC, preferred term, and worst CTCAE grade;
3. Serious TEAEs by SOC, preferred term, and worst CTCAE grade;
4. Study-drug-related serious TEAEs by SOC, preferred term, and worst CTCAE grade;
5. TEAEs associated with drug discontinuation by SOC and preferred term
6. TEAEs associated with dose reduced by SOC and preferred term
7. TEAEs associated with drug interrupted by SOC and preferred term
8. TEAEs associated with death by SOC and preferred term

The number and percentage of subjects with AEs will be also summarized by PT only, if applicable. A by-subject TEAE data listing including, but not limited to, verbatim term, preferred term, SOC, CTCAE grade, and relationship to study drug will be provided.

Listings will be provided for deaths, SAEs, and AEs associated with discontinuation of study drug. A by-subject AE (including treatment-emergent) data listing including, but not limited to, verbatim term, preferred term, system organ class, NCI-CTCAE grade, and relationship to study drug will be provided.

#### 9.4.7.2.2. Adverse Events of Special Interest

The adverse events of special interest (AESI) will be categorized by Standardized MedDRA Queries (SMQs) or grouping of MedDRA terms in this study and will include the following two categories: TdP/other ventricular arrhythmias and Hepatotoxicity. The search criteria for each AESI category are specified in [Table 27](#).

Formatted: C-Hyperlink

**Table 27: AESI Categories and SMQ Search Criteria**

AESI Category	SMQ Search Criteria
TdP/other ventricular arrhythmias	All PTs from Torsade de pointes/QT prolongation SMQ (broad) plus PTs Fall, presyncope, agonal rhythm, arrhythmia, cardiac flutter, paroxysmal arrhythmia
Hepatotoxicity	All PTs from: Cholestasis and jaundice of hepatic origin (SMQ) (narrow) Hepatic failure, fibrosis and cirrhosis and other liver damage-related conditions (SMQ) (narrow) Hepatitis, non-infectious (SMQ) (narrow) Liver related investigations, signs and symptoms (SMQ) (narrow)

The preferred terms (PT) in each AESI category, as well as the AESI categories in the table may be updated. A complete list of AESI categories with PT terms will be reported in the CSR.

The following AESI summaries will be provided:

- TEAEs by AESI category and PT (any TEAEs, Grade  $\geq 3$ , fatal, associated with study drug discontinuation)
- Time to onset of earliest TEAEs by AESI category

#### **9.4.7.2.3. Clinical Laboratory Evaluations**

Descriptive statistics will be provided for selected clinical laboratory test results (hematology and blood chemistry) and changes from baseline by scheduled time of evaluation, including the End-of-Treatment Visit, maximum post-treatment value, and minimum post-treatment value. Both scheduled and unscheduled post-treatment values will be considered for the summaries of the maximum and minimum post-treatment values.

Abnormal laboratory results will be graded according to NCI-CTCAE Version v5.0, if applicable. A shift table, presenting the 2-way frequency tabulation for baseline and the worst post-treatment value according to the NCI-CTCAE grade, will be provided for selected clinical laboratory tests (ALT, AST, Total Bilirubin, ALP, and Creatinine). Both scheduled and unscheduled post-treatment values during the treatment period will be considered.

The number and percentage of subjects with the following potentially clinically relevant abnormal liver function test will be summarized by dose cohort and in subtotal for each part:

- ALT  $\geq 3 \times$  ULN,  $\geq 5 \times$  ULN,  $\geq 10 \times$  ULN, and  $\geq 20 \times$  ULN
- AST  $\geq 3 \times$  ULN,  $\geq 5 \times$  ULN,  $\geq 10 \times$  ULN, and  $\geq 20 \times$  ULN
- Total bilirubin  $\geq 2 \times$  ULN
- Potential Hy's Law cases: ALT or AST  $> 3 \times$  ULN, total bilirubin  $\geq 2 \times$  ULN, and ALP  $< 2 \times$  ULN

Mean absolute neutrophil count and platelet count over time by dose cohort for Part 1 as well as individual absolute neutrophil count and platelet count over time for Part 1A subjects will be plotted.

All clinical laboratory data will be listed, and values deemed clinically significance will be flagged.

